Thirty two participants diagnosed with AD (n=18) and Lewy body dementia (n=14) were given 3.0 grams/day of Feru-guard for 8 weeks. After 8 weeks, the total NPI score was used to evaluate baseline change of behavioral symptoms. In addition, 22/32 participants underwent SPECT imaging at baseline and 8-weeks to evaluate Feru-guard's effect on cerebral blood flow. Participants mean age was 80.6 years and 18/32 (56.3%) were female. Mean baseline NPI score was 21.3 (SD \pm 20.9) and 8-week mean NPI score showed a decrease to 15.9 (SD \pm 14.9). SPECT imaging showed a significant increase in blood_flow in the cingulate gyrus, right frontal lobe, left parietal lobe and brain stem (pons); and significant decrease in blood flow in the left and right occipital lobe. These finding suggests that Feru-guard may improve BPSD in older adults with

AD and LB dementia, changes in cerebral blood flow after 8 weeks on Feru-guard are observed in specific areas of the brain. The authors conclude that the relationship between blood flow changes and improvements in behavioral symptoms warrant further investigation.

C4. Summary of Preliminary data

Preliminary data suggest that that Feru-guard supplementation is relatively well tolerated in older adults with MCI and dementia. Pilot open-label studies suggests that taken for 4-8 weeks, Feru-guard has the potential to improve BPSD as measured by NPI-Q. This study will be the first double-blind, placebo-controlled study to evaluate Feru-guard for BPSD in people with AD, vascular, and mixed dementia and is unique in that it will prescreen for BPSD (at least 3 items on NPI-Q) as part of study inclusion.

D. STUDY DESIGN:

D.1. Overall Study Design

This is designed as a randomized, double-blind, placebo-controlled clinical trial with a 12 week intervention period. Seventy participants with a diagnosis of AD, vascular, and mixed dementia with at least 3 behavioral symptoms present from the Neuropsychiatric Inventory Questionnaires (NPI-Q) will be randomized to the Feru-guard (ferulic acid and Angelica archangelica) or placebo group. Participants will be screened first by a telephone interview or briefly in-clinic and then will be scheduled for an in-clinic screen to establish study eligibility prior to the baseline assessment visit. Clinical and biological outcome measures will occur at baseline and 12 weeks.

D.2. STUDY POPULATION:

D.2.1. Number of Participants

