In the event of a screen failure, all data that has been collected for that participant will be stored identically to data of participants who pass screen and are enrolled into the study. Data handling procedures of participants who are enrolled can be found in Section F of this protocol.

Screen Fail Procedure: Participants who are ineligible for study will be notified at inclinic screening visit and provided an explanation for their ineligibility. The total number of screen failures and justification will be documented.

D.2.4. Vulnerable Populations

The current study will include participants who may be decisionally impaired adults. Dementia is a neurodegenerative disease, which is characterized in part by cognitive decline, so inclusion of decisionally impaired adults is necessary. To protect the rights and welfare of decisionally impaired adults in the study, when possible, informed consent will be obtained. Capacity to give informed consent will be ascertained via discussion and completion of the aid to capacity evaluation (ACE) between the participant, caregiver, and clinician. If it is determined that the participant is unable to give consent, their legally authorized representative (LAR) will be asked to give consent on behalf of the participant. In order to ensure the ongoing protection of the participant's

rights, they will have a committed caregiver accompany them to each visit and assist in the adherence to study procedures, ACE delivered at each onsite visit, and assured that they may withdraw or decline a measure at any time.

D.2.5. Inclusion of Women and Minorities

Including women and minorities in the study will be a priority. Due to the demography of the State of Oregon, we project that the majority of our participants will be "White," and "White not Hispanic or Latino." To maximize the inclusion of minorities, we will recruit from areas that have a high minority population (e.g. Northeast and Southeast Portland) within the Portland metropolitan area.

2010 Oregon Census Data

Gender: 50.5.% female, 49.5% male

Race: 83.6% White, 1.8% Black or African American, 1.4% American Indian and Alaska Native, 3.7% Asian, 0.3% Native Hawaiian and Other Pacific Islander Ethnicity: 11.7% Hispanic or Latino, 88.3% Not Hispanic or Latino

2010 Portland Metropolitan area Census Data

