The visit takes place at OHSU, OCTRI. Participants will attend this visit with their study partner (LAR), and they will bring any medications that they are currently taking. The visit will start with a trained research coordinator going over the consent form and participant rights with participant and their study partner, and answer any questions they have. After going through the consent form, the participant, study partner (who is also the LAR), and the study clinician will go through the ACE to determine the capacity to give consent. If the participant is determined to be unable to give consent, then the LAR will give consent form if they agree to participate in the study. The study partner's signature is necessary because he/she will be answering questions as part of the study procedures.

Demographic information and general medical history, including mental health history, family history and history of allergies will be obtained. Participants will have a general physical and neurological exam, including vital measures (for example, weight and blood pressure).

To determine eligibility for participation, the Neuropsychiatric Inventory Questionnaires (NPI-Q) will be administered, with at least 3 items out of 12 being rated as "present" for inclusion. The NPI-Q is also the primary outcome measure and this will serve as a baseline measure of the participant's BSPD. Additionally, the Mini Mental State Exam (MMSE) will be administered to determine eligibility, with inclusion score of 25 or below. The MMSE will only be used to screen in potential participants.

Randomization will occur after this visit by OHSU Research Pharmacy. The participant will be scheduled for Visit 2 within 14 days.

Baseline (Visit 2): This visit will last approximately 1.5 hour.

This visit will be scheduled within 14 days of the screening visit at OHSU and take place at OHSU, OCTRI. Participants that have met all study inclusion/exclusion criteria will be assigned a study number. Since this visit will be performed close to the screening visit, medical history, NPI-Q, and the physical and neurological examination from the screening visit will be used as "baseline" outcomes and will not be repeated at this visit.

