A fasting blood draw will be performed for safety labs and will include: complete blood count, comprehensive metabolic panel, fasting lipid levels (cholesterol, triglycerides, HDL, LDL), prothrombin time (PT/INR), and for Apo E genotyping. About two tablespoons of blood will be collected. Food/light meal will be provided following the fasting blood draw and after all fasted blood draws throughout the study. In order to establish baseline measures of cognitive function, the Clinical Dementia Rating (CDR) and Montreal Cognitive Assessment (MoCA) will be administered. SF-12 will be filled out by the study partner to establish baseline for general sense of health and ability to perform daily tasks. Because cereals are a source of ferulic acid, we will administer the Dietary Screener Questionnaire (DSQ) to establish a baseline for cereals in the participant's diet. In order to provide an additional measure of caregiver burden, the Zarit Burden Interview (ZBI) screening version will be administered.

Any recent changes in medications (prescribed, over-the-counter medications, nutritional supplements, herbals) and any recent changes in diet will be recorded at this visit. Adverse events will be collected at baseline for comparison throughout the study. The study coordinator will dispense a 12-week supply of medication and give both verbal and written instructions on medication dosing.

Week 6 (Visit 3 - Phone): This visit will last approximately 0.5 hour.

This visit will take place over the phone, six weeks after the baseline visit. The study coordinator will record adverse events and any recent changes in medications (prescribed, over-the-counter medications, nutritional supplements, herbals) and any recent changes in diet. Study supplement compliance will be assessed for by asking the participant how many capsules they take a day and have they stopped taking the capsules for longer than 24 hours. If possible, the coordinator will schedule the week 12 visit with the participant.

Week 12 (Visit 4): This visit will last approximately 2.5 hours

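### Randomising after Visit 1 opens a gap of up to 14 days in which people can leave already randomised but undosed, without secondary baselines or the Apo E covariate

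*Combined protocol and SAP*

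**What the plan says.** Section E.2 sets the order of events. Under the screening visit: "Randomization will occur after this visit by OHSU Research Pharmacy", and then "The participant will be scheduled for Visit 2 within 14 days". The exact day of randomisation is not fixed, so 14 days is the maximum gap.

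The primary baseline is taken at screening: "The NPI-Q is also the primary outcome measure and this will serve as a baseline measure". The rest is first collected at Visit 2: "In order to establish baseline measures of cognitive function, the Clinical Dementia Rating (CDR) and Montreal Cognitive Assessment (MoCA) will be administered". The same visit covers the SF-12, ZBI, dietary questionnaire, safety bloods, Apo E sample and dispensing, and Table 4 agrees.

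On eligibility, section D.1 says that people are "scheduled for an in-clinic screen to establish study eligibility prior to the baseline assessment visit", and section D.2.3 says: "Participants who are ineligible for study will be notified at inclinic screening visit". Under Visit 2, section E.2 adds: "Participants that have met all study inclusion/exclusion criteria will be assigned a study number".

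Section G.3 allows for 10% loss and ties it to the 12 weeks. Section D.2.1 states the same 10% against 70 enrolled, without that limit. Section G.2 plans a mixed model that is valid if data are missing at random, and lists Apo E4 genotype among the adjustment variables. No section defines an analysis set or says what happens to people who are randomised but never dosed.

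**The concern.** Someone who withdraws between the two visits already holds an allocation. That person has a baseline NPI-Q but no capsules, no MoCA, SF-12 or ZBI baseline and no Apo E result, and may well have no week-12 assessment. If such people are left out, the analysis no longer covers everyone randomised. If they are kept, they contribute little information. If they were not counted in the 10%, the trial ends with fewer completers than planned.

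All of this follows from allocating before it is needed. Nothing at Visit 2 before dispensing depends on the allocation.

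**Working it through.** **Inputs.** Section G.3 and Table 6: difference 7 points, SD of change 9.7, 80% power, significance level 0.05, 31 per group in the table and 32 in the text, 70 in total, 10% dropout. These are taken as the plan gives them. The share lost in the gap, g, is not in the documents. I assume 3%, 5% and 10%.

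**Reproducing the plan.** With n = 2(z₀.₉₇₅ + z₀.₈₀)² × SD² / difference² and (1.960 + 0.842)² ≈ 7.849:

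- 10 points: 2 × 7.849 × 94.09 / 100 = 14.8, so 15
- 7 points: 2 × 7.849 × 94.09 / 49 = 30.1, so 31
- 6 points: 2 × 7.849 × 94.09 / 36 = 41.0, so 42

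All three rows of Table 6 reproduce with a two-sided test. Allowing for dropout, 31 / 0.9 = 34.4, so 35 per arm and 70 in total. Starting from 32, 32 / 0.9 = 35.6, so 36 per arm and 72 in total.

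**Slack.** 70 × 0.9 = 63 completers, or 31.5 per arm. Table 6 needs 62 and the text implies 64. The plan is one person over on the first count and one short on the second.

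**Effect of the gap.** Completers per arm = 35 × (1 − g) × 0.9, with gap losses having no week-12 outcome. Power is from the two-sided two-sample t-test with non-centrality (7 / 9.7) × √(n / 2).

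| Assumed g | People lost of 70 | Completers per arm | Power for 7 points | Difference detectable at 80% power | Total to keep 31 per arm |
|---|---|---|---|---|---|
| 0 | 0 | 31.5 | 80.5% | 6.96 | 70 |
| 3% | 2.1 | 30.6 | 79.2% | 7.07 | 72 |
| 5% | 3.5 | 29.9 | 78.4% | 7.14 | 74 |
| 10% | 7.0 | 28.4 | 76.1% | 7.35 | 78 |

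The last column is 2 × 31 / ((1 − g) × 0.9), with each arm rounded up.

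**Covariate.** Section E.7.2 draws Apo E only at Visit 2, and section G.2 adjusts for it. No imputation is described. A person lost in the gap would therefore drop out of a model that needs every covariate, even though a baseline NPI-Q exists.

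**Sequence of terms.** Section E.5 describes the randomisation scheme as being for new enrolments. Section F.1 assigns the identification number at enrolment. Section E.2 assigns the study number under Visit 2. If these are the same number, enrolment is at Visit 2, yet randomisation comes before it. Section D.1 counts 70 randomised and section D.2.1 counts 70 enrolled. With any loss in the gap, these are different totals.

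**The case against.** A reader might infer from the study-number sentence under Visit 2 that people are randomised before their eligibility is known. The documents do not support that. Sections D.1 and D.2.3 place eligibility at the screening visit. The NPI-Q, MMSE, history and examination are all done there, and no criterion names a Visit 2 result. The sentence can be read as numbering people already found eligible. Medication changes are recorded at Visit 2, but no re-check of eligibility is described. Withdrawal is the one clear route of loss.

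A reader might also compute a diluted effect, with people who were never dosed analysed as having none. On 31.5 per arm that gives power of about 78%, 76% and 72% at 3%, 5% and 10%. It needs week-12 NPI-Q data from people who left before receiving capsules. Section E.3 lets people stop the supplement and stay for assessments, so such data are possible, but the documents give no reason to expect them from this group.

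The strongest case against the point is that the gap is short, the primary baseline precedes randomisation, the mixed model can in principle keep people with only a baseline, Aim 2 is called exploratory, and the trial is a pilot. In addition, if the 70 in section D.2.1 are counted at Visit 2, gap losses fall outside the 70 and the power loss does not arise.

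Most of this stands and limits the size of the point. It does not remove it. A lone baseline says almost nothing about 12-week change, the missing Apo E value works against keeping that person in the adjusted model, and section D.1 counts the 70 as randomised. The text does not settle which count applies.

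**Conclusion.** The point holds as a cheap improvement. Allocation comes up to 14 days before the secondary baselines, the Apo E sample and dispensing, and the plan does not say how people lost in between are counted or analysed.

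The expected harm is reduced precision. Participants and study staff do not know the allocation and no capsule has been taken, so loss in the gap should not differ by arm. For the same reason, the Visit 2 baselines of those who attend remain sound.

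The cost is about 1, 2 or 4 points of power at 3%, 5% or 10% loss. These rates are assumptions, and the result also assumes that the 70 are counted at randomisation and that the 10% covers only the 12 weeks. Small as it is, the loss takes power below the stated 80% at each of these rates, because the plan has almost no slack.

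**What to change.** Move randomisation to Visit 2. Possible wording for section E.2: *Randomisation takes place at Visit 2, once eligibility has been reconfirmed and all baseline assessments and blood samples are complete, immediately before the capsules are dispensed.* Every baseline then precedes allocation, and people who leave after screening are not randomised losses.

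Reconcile the wording on eligibility, enrolment, randomisation and study number in sections D.1, D.2.1, D.2.3, E.2, E.5 and F.1, so that the 70 refers to one defined event.

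If the timing has to stay, define the analysis set for people randomised but not dosed, state how a missing Apo E value is handled, and say whether the 10% includes losses before Visit 2.

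The cost of the main change is protocol wording and one operational demand: the Research Pharmacy must release the allocated kit on the day of Visit 2.

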OHSU VA: Collaborative Dementia Care at the VA Portland Health Care Systems includes four geriatric neurologists, two geriatric medicine specialists and three geriatric psychiatrists. Patients are seen in five outpatient clinics during the week. Patients come from Veterans Administration clinics throughout Oregon and Southern Washington. In addition to clinic care, we provide Telehealth consultative dementia care with sites throughout Oregon and Washington. Physicians in our program have academic teaching and research appointments at OHSU.

D.4. Recruitment Methods

Prior to recruitment, the joint VAPORHCS-OHSU IRB will approve this study for human study. After receiving IRB approval, potential study participants will be found through database searches, and clinic referral for an estimated 6 month long enrollment period. Recruitment will be primarily focused on the Portland metropolitan area, though participants from outside the area will be enrolled if they are able to travel to OHSU. A blinded scan of the OHSU clinical database can identify potential participants that have visited OHSU in the last year that will meet the study's inclusion/exclusion criteria. Individuals identified through medical record scans will be sent an IRB approved letter describing their potential eligibility for the study. We will also utilize NeuroNext database of people that have consented to be contacted about clinical trial opportunities at OHSU. In addition, patients from the OHSU VA and NIA-Layton Aging & Alzheimer's Disease Center clinics who are potentially eligible for the study will be referred for screening. VA Portland Health Care System Neurology Dementia, geriatrics clinics, geriatric psychiatry clinic and Layton Aging & Alzheimer's Disease Center have over 20 patients per week with dementia diagnosis. We expect that we could obtain at least 5 participants per week on average who meet our inclusion criteria and consent to this study (20 participants per month). The last participant is expected to be enrolled at the end of 6 months from the start of the recruitment, which allows the last recruited participant to finish the trial within 1 year.

		Year 1							Year 2						
Month	1	2	3	4	5	6	7	8	9	10	11	12	1	2	3
IRB Approval															
Study Enrollment															
Blinded															
Treatment															
Intervention															
Data Analysis															

Study Timeline:

D.5. Compensation

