This is a double-blind, placebo-controlled study. The placebos will be matched to the active supplement in both sensory and physical characteristics. The participants, study investigators, research associates, and study coordinators will have no knowledge of study assignment. Data analysis will be performed blinded to treatment status. The OHSU Research Pharmacy will be responsible for establishing a randomization scheme for newly enrolled participants. Additionally, the Research Pharmacy will ensure blinding of all study medications. We will also evaluate the effectiveness of our blinding by giving study evaluators, participants, study partners, and investigators a short questionnaire asking about knowledge of group assignment. The randomization code will be broken only after data analysis or if there are numerous serious adverse events before the end of the study.

E.6. Compliance

Compliance will be measured informally by a phone check week 6 (i.e., asking how participant is doing taking the supplement). If the participant is not taking the supplement in the appropriate dosage or stopped taking the capsules for longer than 24 hours, the coordinator will speak with the participant about finding ways to increase compliance. Official compliance will be measured in-clinic at Visit 4 via packet count. A participant will be considered compliant if they are \geq 80%.

E.7. Description of Assessments and Procedures E.7.1. Cognitive, Functional, Behavioral Assessments

Neuropsychiatric Inventory Questionnaire (NPI-Q)

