The study will be monitored by the Data Safety and Monitoring Board (DSMB) of the Oregon Center of Complementary and Alternative Medicine in Neurological Disorders (ORCCAMIND) once a year to ensure participant safety. If a participant reports serious side effects related to the study medication and information on group assignment is believed to be necessary for the participant's safety and well-being, the blind will be broken for that participant. The randomization code will otherwise be broken only after data analysis or if there are numerous reports of serious adverse events before the end of the study. The DSMB has been and will continue to be compliant with NIH Policy for Data and Safety Monitoring.

I.2. Adverse Events

Adverse events (AEs) will be monitored at visits 2-4 as a part of the clinic visits and by phone. Although assessment of adverse events will also include solicitation of non-specific change (e.g., "Do you feel different since beginning the treatment?"), a 12 item adverse events checklist covering all major organ systems will be included to probe for adverse events. The nature of each AE, its severity (mild, moderate, or severe), its likely relationship to study treatment (definite, probable, possible, not related, or unknown), its duration and any necessary treatment modifications or adjustments will be recorded. In addition to recording of AEs, labs to assess basic metabolic function (including liver function tests), plasma lipid levels, a complete blood count, and prothrombin time (PT/INR) will be performed at visit 2 and 4. Participants will be reminded and encouraged during clinic visits and phone checks to contact the study coordinator or a study investigator as soon as a moderate or serious adverse event should occur.

J. RISKS AND BENEFITS

J.1. Potential Risks

Venipuncture: The risks are minimal and may include some pain, bleeding and transient hematomas.

Questionnaires: The risk from filling out questionnaires is minimal; there may be mild anxiety from filling out questionnaires.

Feru-guard: At a daily dose of 360.64 mg ferulic acid and 40.02mg Angelica archangelica per day, the risks are minimal. In previous studies, skin rash and gastrointestinal side effects (constipation, diarrhea) are included as potential side effects. Due to unknown interactions with pharmaceutical medications, we will exclude participants on blood thinning medications (e.g. warfarin) to mitigate risk.

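### Yearly DSMB monitoring does not guarantee a board review during the 26-40 weeks of dosing, and the only trial-level response to SAEs is an undefined code break with no named recipient

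*Combined protocol and SAP*

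**What the plan says.** Section I.1 has an existing DSMB monitor the study "once a year to ensure participant safety". It gives no date for the first review and no provision for an unscheduled one.

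Section D.4 plans about six months of enrolment on a timetable that "allows the last recruited participant to finish the trial within 1 year". It also expects "at least 5 participants per week on average who meet our inclusion criteria and consent to this study". Section E.2 adds "The participant will be scheduled for Visit 2 within 14 days" after screening, and at that visit: "The study coordinator will dispense a 12-week supply of medication". The only scheduled contact between then and week 12 is the week-6 telephone call.

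The documents give two responses to SAEs:

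- **Individual (I.1).** For a person with a serious event linked to treatment, the rule applies where "information on group assignment is believed to be necessary for the participant's safety and well-being, the blind will be broken for that participant".
- **Trial level (E.5 and I.1).** E.5 states: "The randomization code will be broken only after data analysis or if there are numerous serious adverse events before the end of the study". I.1 repeats it: "The randomization code will otherwise be broken only after data analysis or if there are numerous reports of serious adverse events".

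Section I.2 asks participants to contact the coordinator or an investigator promptly about moderate or serious events, and it grades relatedness. It describes no onward report to the DSMB.

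**The concern.** The interval between board reviews is longer than the whole dosing period. If the plan is followed exactly, all 70 participants could start and finish the supplement without the board looking at accumulating safety data.

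The only provision that could act sooner is the code break. It has no threshold, decision maker or recipient, and no consequence such as a pause or stop. Unblinding one participant protects that person but gives no comparison between arms. The coordinators and investigators who receive event reports are blinded, so they cannot make that comparison either.

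Participants have dementia, some will be enrolled on a representative's consent, and safety is part of the primary aim (section A). Section B.4.2 acknowledges that little published trial safety data exist for one of the two active ingredients.

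**Working it through.** **1. Length of the dosing period.** Inputs: 70 participants (D.2.1), 12 weeks each (D.1), accrual of 5 per week or six months, taken as 26 weeks (D.4), and up to 2 weeks from screening to baseline (E.2).

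- Shortest: 70/5 = 14 weeks of accrual; 14 + 12 = 26 weeks (28 with the full baseline window).
- Longest: 26 + 2 + 12 = 40 weeks.

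Both agree with the plan's own statement that the last participant finishes within a year.

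**2. Chance that no yearly review falls within dosing.** Assumption: reviews are 52 weeks apart and their dates are unrelated to study start. For a dosing period of W weeks the chance is 1 - W/52.

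- W = 40: 1 - 40/52 = 0.23.
- W = 26: 1 - 26/52 = 0.50.

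So a review falls somewhere within dosing with probability 0.50 to 0.77. That includes dates in the first or last weeks, when few data have accrued or few participants are still on supplement.

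**3. Expected number of SAEs.** Section C.1 supports only a range.

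*(a) Pooled studies, scaled for exposure.* C.1 reports 4 SAEs among 244 participants. Assuming everyone was followed for the duration in Table 2, person-weeks are:

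20 x 4 + 28 x 96 + 64 x 52 + 90 x 104 + 22 x 48 + 20 x 104
= 80 + 2,688 + 3,328 + 9,360 + 1,056 + 2,080 = 18,592.

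This trial has 70 x 12 = 840. Expected SAEs = 4 x 840/18,592 = 0.18. Poisson P(at least 3) = 0.0009, about 0.1%.

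*(b) The AD/Lewy body study alone.* This is the earlier study in Table 2 that included AD: 64 participants over 12 months. Table 3 lists 4 deaths and 1 stroke.

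- 4 events: 70 x 4/64 x 12/52 = 1.01; P(at least 3) = 0.08.
- 5 events: 70 x 5/64 x 12/52 = 1.26; P(at least 3) = 0.13.

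Both rates come from events linked to dropout, so SAEs in participants who stayed on study may be missing. Most studies in (a) enrolled people with mild cognitive impairment, not dementia.

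**4. Would a review tied to week-6 calls fall within dosing?** Take the date when 35 of the 70 have had that call, with even accrual.

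- At 5 per week: 35/5 + 6 = week 13, or week 15 with the full baseline lag, against a last dose at week 26 or 28. By then 13 x 5 = 65 have started, 5 have finished, 60 are on supplement and 5 have yet to start.
- At 70/26 = 2.69 per week: 13 + 6 = week 19, or 21 with the lag, against a last dose at week 38 or 40. By then 19 x 2.69 = 51 have started, 7 x 2.69 = 19 have finished, 32 are on supplement and 19 have yet to start.

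In both cases the review comes midway through dosing, when a recommendation could still protect most or many participants.

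**The case against.** The strongest reply is that this is a small, short pilot of a supplement with few expected SAEs, under a board that already exists and states compliance with NIH monitoring policy. The first review date is not given, so one may well fall within dosing. Board procedures or duties under the planned IND (B.5.1) may already provide for prompt reporting and ad hoc review. Participants are told to report events promptly, and individual unblinding covers an urgent case at any time. All of that stands, and it keeps the point modest. None of it puts a board review within dosing, or a route from an event report to the board, into this protocol.

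Two stronger readings should be resisted.

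- A reader might infer that the code break would unblind site staff or study partners and so bias the caregiver-rated NPI-Q. The documents do not say this. E.5 and G.4 state that participants and study staff have no knowledge of assignment, and I.1 places the code break in the DSMB section. Disclosure beyond the board could be inferred only from silence.
- A reader might take the 3 versus 1 deaths in Table 3 as a sign of harm. The groups are not identified, C.1 reports no significant difference between them, and Table 2 lists the study as a crossover. The figures settle the direction of risk neither way.

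**Conclusion.** The concern holds as a gap in safety monitoring. The yearly schedule guarantees no board review within a dosing period of 26 to 40 weeks. On the assumption of unrelated dates, the chance of none is 23% to 50%. It does not follow that no review will occur: the first review date is simply not stated. The sole trial-level SAE provision lacks a threshold, a decision maker, a recipient and a consequence.

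The expected burden is small, about 0.2 to 1.3 SAEs, with a 0.1% to 13% chance of three or more. Those figures rest on dropout-related events and assumed full follow-up, so they are rough. Because counts will be low, an SAE trigger alone would often not fire and would leave the scheduling gap open; a review timed within dosing is also needed. The change is worth making as an inexpensive safeguard.

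**What to change.** 1. **I.1, timing.** Add one DSMB safety review within dosing, for example when about half of the 70 participants have had their week-6 call. Keep the yearly review.
2. **I.1, reporting.** Send each SAE to the DSMB as it occurs. Hold an ad hoc review for any SAE rated definite, probable or possible on the I.2 scale, or when SAEs reach a count agreed with the DSMB before first enrolment.
3. **I.1 and E.5, code break.** Replace the early code break for *numerous* SAEs with an arm-level listing sent by the Research Pharmacy to the DSMB only. The DSMB then recommends continue, pause or stop. State that participants, study partners, raters, investigators and analysts stay blinded. Leave individual unblinding as written.

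Cost: wording in two sections, one additional scheduled board review, an occasional ad hoc review, and listings from the Research Pharmacy, which already holds the randomization scheme. No participant visits are added.
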